
2. Objectives (include all primary and secondary objectives)

Aim 1: Evaluate the magnitude and duration of cannabinoid/opioid combination to reduce clinical pain and central sensitization. We hypothesize the cannabinoid/opioid combination will increase the

magnitude and duration of analgesia in clinical pain report (Hyp1) and QST-derived central sensitization (Hyp2), relative to each drug administered alone and relative to placebo.

Aim 2: Evaluate the degree to which physical functioning is altered by the cannabinoid/opioid combination. We hypothesize that the drug combination will improve physical function (Hyp3) relative to the drugs administered alone and placebo.

Aim 3: Compare the subjective, physiological, abuse liability, and cognitive effects of the cannabinoid, opioid, and combination. We hypothesize that cannabinoids will not increase adverse events (Hyp4), or abuse liability (Hyp5: ratings of positive drug effects) relative to opioids alone and that the cannabinoid (alone and in combination with opioids) will reduce neurocognitive performance (Hyp6), relative to the opioid alone and placebo.

Aim 4: Evaluate the pharmacokinetic and pharmacodynamic profile of the cannabinoid, opioid, and the combination in OA patients. We hypothesize that the combined dose will result in an altered pharmacokinetic (Hyp7) /pharmacodynamics profile (Hyp8) compared to either drug alone.

3. Background (briefly describe pre-clinical and clinical data, current experience with procedures, drug or device, and any other relevant information to justify the research)

This laboratory study is the first step in addressing an important and timely public health problem: Can cannabinoids enhance the analgesic efficacy of an opioid and ultimately reduce opioid dosing in people with chronic pain?

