Cold Pressor Testing and CPM: A series of procedures designed to elicit and measure endogenous inhibition of pain will be applied. Subjects will undergo a series of cold pressor tasks (i.e., the conditioning stimuli) consisting of immersion of the hand in a circulating cold water bath. During hand immersion, pressure responses or temporal summation will be re-assessed while subjects' hands remain in the cold water. Subjects may remove their hand at any time. Two minutes after finishing the first immersion, subjects will re-immerse their hand in the water, and one of these tests (pressure response or temporal summation) will be re-assessed, each separated by 2 min (the tests will be conducted in random order). A CPM Index is quantified as the average percent change (across trials) in PPT_h or TS during the cold pressor tasks relative to baseline ratings¹¹⁹. One final cold-water immersion will be performed at the conclusion of the CPM procedures. This will involve a typical cold pressor task, using immersion of the hand until the subject's tolerance is reached, with a 5-minute uninformed time limit.

CS: Temporal summation measures, CPM, and after-sensation responses to these measurements will be combined to create the CS index for use in statistical analyses for which we have previously published⁵⁷. Physical Performance Measures will objectively assess physical functioning. Patient self-report of activity relates only modestly to performance measures on standardized physical tests¹²⁰⁻¹²⁵ and physical performance under the effects of the drugs administered here are an essential test of the real-world applicability of administering such analgesic combinations in the natural environment. This set of tests will involve a Timed Up and Go (TUG) test. Stair climb (which includes hand rails) and a three-Minute Walk (3MW) test, all commonly used measures of KOA physical function¹²⁶. The TUG test measures the time it takes a subject to rise from a standard chair, walk 3m, and then return to sitting in the same chair. In the 3MW test, subjects are asked to cover as much distance as possible in 3 minutes while walking laps on a standardized indoor course. Each test will be conducted at baseline and at projected peak effect to avoid participant fatigue.

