a. Primary outcome variable:

Aim 1: Evaluate the magnitude and duration of cannabinoid/opioid combination to reduce clinical pain (Hyp1) and central sensitization (Hyp2). Hyp1 (pain VAS) and Hyp 2 (CS) will be analyzed using repeated 2-factor (Drug x Time) models that examine linear and quadratic effects as well as duration and magnitude, and direct and interaction effects. If large variation exists across subjects at baseline, then raw data will be transformed to change-from-baseline and analyzed in drug condition by time models. A secondary outcome will be peak change from baseline, analyzed as a function of Drug (1-factor model).

- Aim 2: Evaluate the degree to which physical functioning is altered by the cannabinoid/opioid combination.** Hyp3 will be assessed using the TUG and 6MWT. Time to complete the TUG task will be the primary outcome and will be evaluated using 2-factor (Drug x Time: Pre to Peak) models.
- Aim 3: Conduct a direct comparison of the subjective, physiological, abuse liability, and cognitive effects of the cannabinoid, opioid, and combination.** Hyp4 (adverse events) will be assessed by summing the mean number of related mild, moderate, and severe adverse events (separately) and using 1 factor models to assess a main effect of Drug. Hyp5 (abuse liability) will be assessed using the Drug vs. Money questionnaire and changes in VAS ratings using 2-factor models (Drug x Time). Hyp6 will evaluate changes in neurocognitive performance, including study session number as a covariate to control for practice effects, using 2-factor (Drug x Time) analyses. Secondary outcomes for this hypothesis will be analysis of peak change from baseline for the cognitive outcomes, analyzed using 1-factor (Drug) ANOVAs to evaluate a main effect of drug.

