- Aim 4: Evaluate the pharmacokinetic (pK) and pharmacodynamic (pD) profile of the cannabinoid, opioid, and the combination in OA patients.** Hyp 7 (pK) will be assessed by evaluating Cmax (maximum concentration) and Tmax (time to maximum concentration) as a function of Drug condition using 1-factor models. We will also examine linear and quadratic effects to evaluate the time course of concentration. Linear and quadratic effects will be modeled for Hyp8 (pD) and analyzed by evaluating VAS and physiological ratings, transformed to change from baseline, evaluating area under the curve and peak change from baseline to identify main effects of the Drug condition. We will then conduct multivariate regression analyses to evaluate the degree to which the Cmax and Tmax correlate with pharmacodynamic outcomes, including abuse liability ratings, VAS ratings of drug effects, and cognitive testing outcomes.

Statistical analyses will be conducted separately by Phase and use multilevel analyses with an autoregressive (AR1) or compound symmetry (CS) covariance structures (as appropriate for the data set) using SAS PROC MIXED¹³⁷. Interpretation of drug condition main effects and interactions will rely on Tukey post-hoc tests. Statistical significance will be set at $p < 0.05$.

Expected Outcomes: We expect that dronabinol will enhance hydromorphone-induced analgesia to both clinical and laboratory-evoked pain. Our comprehensive battery of rigorous, testing procedures provides an opportunity to test effects on multiple mechanisms of experimentally-induced pain. We also expect improvement in physical functioning under combined dosing, and that the addition of the cannabinoid will not significantly increase the overall abuse liability or adverse event profile. We do suspect the cannabinoid may have cognitive effects (though the degree to which this may happen is not clear).

b. Secondary outcome variables.

Demographic and drug use characteristics that are hypothesized a priori to be associated with outcomes (e.g., Body Mass Index) will be compared across sex groups and significant differences will be included as covariates in the subsequent analyses. All analyses will be repeated and sex (male/female) will be added as a factor to the analyses.

c. Statistical plan including sample size justification and interim data analysis.

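### The plan does not say which term of the Pre/Peak TUG model tests Hyp3, and one of the two terms it will interpret estimates only half the drug effect at peak

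*Combined protocol and SAP*

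**What the plan says.** Section 2, Aim 2 sets the hypothesis: "We hypothesize that the drug combination will improve physical function (Hyp3) relative to the drugs administered alone and placebo". Section 7.a, Aim 2 names the outcome, "Time to complete the TUG task will be the primary outcome", and the analysis, "evaluated using 2-factor (Drug x Time: Pre to Peak) models".

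Section 4.a (Physical Performance Measures) gives the schedule: "Each test will be conducted at baseline and at projected peak effect to avoid participant fatigue". Section 4.a (Experimental Sessions) puts the baseline measures at about 0930 and dosing at about 1100. Time therefore has exactly two levels, and the first precedes that session's drug.

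The methods paragraph of Section 7.a, which covers all aims, adds: "Statistical analyses will be conducted separately by Phase and use multilevel analyses with an autoregressive (AR1) or compound symmetry (CS) covariance structures", and then "Interpretation of drug condition main effects and interactions will rely on Tukey post-hoc tests". Neither that paragraph nor Aim 2 says which term decides Hyp3.

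No baseline covariate, and no constraint of equal pre-dose means, is stated for Hyp3. The option beginning "If large variation exists across subjects at baseline, then raw data will be transformed to change-from-baseline" is written under Aim 1. One-factor peak-change analyses are given for Aim 1 and Hyp6, and a session-number covariate for Hyp6 only.

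Section 4.a (Study Design Overview) fixes hydromorphone alone as the first session and randomizes the order of the other three conditions.

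**The concern.** Hyp3 asks one thing: how TUG differs between conditions once the drugs are acting. A Drug main effect over Pre and Peak does not answer that, because half of what it averages was measured before dosing. If Hyp3 were judged on it, a real improvement could be missed, and one that was detected would be reported at half its size.

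The interaction does target the right quantity. With two time levels it is a difference in change scores, and it pays for the full noise of the pre-dose value. With both terms open to interpretation and neither named, the Hyp3 result could depend on a choice made after the data are seen.

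**Working it through.** **The plan's own figure.** Section 7.c gives 10 to 15 individuals for large effects, for CPM and cold pressor. The effect sizes are not printed. Cohen's conventional large values reproduce both ends: a two-sided paired t test with d = 0.8 gives 15, and a four-level repeated-measures ANOVA with f = 0.4 and correlation 0.5 gives 10. No such figure is given for TUG.

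**Inputs.** Two TUG values per session and alpha 0.05 come from the plan; two-sided testing is assumed. The TUG effect, SD and correlations are not given. Let r be the correlation between pre-dose and peak residuals within a session after removing the participant effect: r = (within-session correlation − between-session correlation)/(1 − between-session correlation). It is an assumption, shown over a range. n = 32 per Phase is 64 completers divided by 2; Section 7.c does not say whether 64 is per Phase or in total.

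**Contrasts.** For two conditions, take each participant's pre-dose difference and peak difference, with unit residual SD and true peak effect D. Each difference has variance 2, and their covariance is 2r.

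- Drug main effect: mean (0 + D)/2 = D/2; variance (2 + 2 + 4r)/4 = 1 + r.
- Drug x Time interaction: mean D; variance 4(1 − r).
- Peak adjusted for pre-dose value: mean D; variance 2(1 − r²).

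Information is mean²/variance. The sample size needed relative to adjusted peak is therefore

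- main effect: 4(1 + r)/[2(1 − r²)] = 2/(1 − r);
- interaction: 4(1 − r)/[2(1 − r²)] = 2/(1 + r).

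Power below is from the noncentral t with n = 32 and no Tukey adjustment. D is set so that adjusted peak has 80% power.

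| r | D (residual SD) | Main effect: N ratio, power | Interaction: N ratio, power |
|---|---|---|---|
| 0.2 | 0.71 | 2.5, 43% | 1.67, 58% |
| 0.3 | 0.69 | 2.9, 38% | 1.54, 62% |
| 0.5 | 0.63 | 4.0, 29% | 1.33, 68% |

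Because D is calibrated to 80%, these powers are almost the same at n = 50 or 64.

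**Simulation check** (4,000 replicates, n = 50, between-session correlation 0.70, within-session 0.85, so r = 0.15/0.30 = 0.5; D = −0.30 SD). The main effect estimated −0.15 with 35% power. The interaction estimated −0.30 with 77%, and adjusted peak −0.30 with 87%.

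**Session 1.** Suppose session 1 differs by an additive shift c that is equal before dosing and at peak. In a comparison with hydromorphone alone the bias is (c + c)/2 = c for the main effect, c − c = 0 for the interaction, and c − rc = (1 − r)c for adjusted peak. A null simulation with c = 0.20 SD and r = 0.5 (same n and correlations) gave:

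| Contrast | Bias (SD, absolute) | Rejections at 5% |
|---|---|---|
| Drug main effect | 0.20 | 54% |
| Adjusted peak | 0.10 | 17% |
| Drug x Time | 0.00 | 4.8% |

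**The case against.** A reader might infer that the plan tests Hyp3 on the Drug main effect. The documents do not say so. The Pre-to-Peak label points more naturally to the interaction, and the sentence on main effects and interactions serves all aims, including one-factor models where the main effect is the only term. The 29% to 43% powers therefore describe what happens if that term is used. What stands is that nothing excludes it for Hyp3.

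A reader might also infer that the interaction wastes the baseline. It does not: it uses the baseline, is unbiased for the full effect, and loses only efficiency, by a factor between 1 and 2 for r from 0 to 1 that shrinks as r rises (1.14 at r = 0.75). Nor is modelling the baseline as an outcome wrong in itself. A model holding pre-dose means equal across drugs would be efficient, but the plan states no such constraint.

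There is a third reading. Tukey tests of the interaction could mean pairwise comparison of the eight Drug x Time cells, which includes combination versus comparator at Peak. That contrast estimates the full effect, and at r = 0 it matches adjusted peak before multiplicity (both about 76% power at n = 50 with all correlations 0.70 and D = −0.30 SD). This stands as a possible reading. It brings 8 × 7/2 = 28 pairs, none of which is a difference in change, and it keeps any session-1 shift in full.

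The strongest objection is to adjusting for baseline in every comparison. Because hydromorphone alone is always session 1, that would leave (1 − r) of an additive session shift where the planned interaction leaves none. This is correct, and the fix below separates the comparisons accordingly.

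Finally, a weak TUG test would not leave function unexamined: a walk test, stair climb, WOMAC disability and BPI interference are also collected. TUG is nevertheless the named primary outcome for Hyp3.

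**Conclusion.** The point holds as a gap in specification with a measurable cost. The halving of the Drug main effect is exact whenever expected pre-dose values are equal across conditions, and it does not depend on r. That term also takes any additive session-1 shift in full in comparisons with hydromorphone alone. The interaction is valid for the full effect and costs 1.33 to 1.67 times the sample of adjusted peak at r = 0.5 to 0.2.

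The power figures rest on assumed r, equal SDs before dosing and at peak, and no multiplicity adjustment. The freedom from bias of the change score in the hydromorphone-alone comparison rests on a session shift that is the same before dosing and at peak; a shift that differs within the session would not cancel. The documents do not support a claim that the planned Hyp3 test is the diluted one, only that the plan leaves it available.

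**What to change.** In Section 7.a, Aim 2:

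1. State that the single Hyp3 estimand is the drug difference in TUG time at peak, and that the Drug main effect of the Pre/Peak model supports no Hyp3 conclusion.
2. For combination versus placebo and versus dronabinol alone (sessions 2 to 4, randomized order), analyse peak TUG with Drug and session as factors and that session's pre-dose TUG as a covariate.
3. For combination versus hydromorphone alone, use the change-from-baseline (Drug x Time) contrast. State that session and drug cannot be fully separated here, because no other condition occurs in session 1; a session term does not solve this.
4. Say how the multiplicity adjustment applies to these three comparisons, since they no longer come from one four-level model.

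No new data are needed. The cost is some extra analysis wording and, for the hydromorphone-alone comparison only, the efficiency loss of 2/(1 + r) relative to covariate adjustment. That loss is accepted in exchange for removing an additive session shift.

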Study Design Overview: We propose to study the separate and combined effects of the FDA-approved cannabinoid dronabinol (Marinol) and the prototypical opioid hydromorphone (Dilaudid). Following telephone and screening to establish study eligibility, a cohort of **n=100** adults with knee osteoarthritis (KOA) will complete four different within-subject experimental sessions. Participants will complete one of two Phases, receiving either a 4mg or 2mg dose of hydromorphone. Randomization will be split equally across the two Phases. During each session, participants will complete baseline QST, questionnaires, and a neurocognitive battery. Oral hydromorphone will be administered in the first session. Subsequent sessions will consist of 1 of 3 conditions, and session order will be randomized and counter-balanced. Conditions will be 1) placebo; 2) oral dronabinol (10mg); and 3) combined hydromorphone and dronabinol (10mg). Measures will be repeated throughout the session to fully characterize the drug effects. Participants and staff will be kept blinded to the study medications under investigation, and participants will be informed in the consent form they may receive a combination of FDA-approved stimulants, benzodiazepines, opioids, cannabinoids, over-the-counter medications or placebo, though the participants will not actually be receiving stimulants, benzodiazepines, or over-the-counter drugs. All participants will be provided with transportation to and from the experimental sessions. Primary outcomes are measures of clinical pain, central sensitization, physical function and drug effects/adverse events. A subset of participants will undergo blood draws for pharmacokinetic (pK) profile. This will be voluntary and should aid recruitment as those that do not want an IV will still be allowed to participate in the study. We will aim to recruit 30 participants that volunteer to undergo IV/blood drawing procedures in order to characterize pK.

Phase 1: The initial Phase of this project will include hydromorphone at a dose of 4mg.

Phase 2: The second Phase of this project will include hydromorphone at a dose of 2mg in order to evaluate drug effects at a reduced opioid dose.

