| Randomized Order | | |
| 2 | 0 (placebo) | 0 (placebo) |
| 3 | 0 (placebo) | 10mg |
| 4 | 4mg | 10mg |

approximately 0930 participants will complete baseline QST, physical functioning measures, and self-report measures (see below). The second 10-14mL blood draw (for those in the pK group) will be collected and then two oral capsules containing either active drug or placebo (randomized in sessions 2-4) will be administered at approximately 1100. Briefly, subjects will complete QST, physical functioning, cognitive testing, self-report, and vital sign measures (as well as blood draws for those in the pK group) at regular intervals following study drug administration. Self-report measures will include specific opioid agonist and antagonist effects, to assess whether cannabinoids

are exerting an effect on a particular category of opioid agonist symptom, and will capture whether any negative effects (e.g., nausea) occur. Frequent collection will enable evaluation of time to peak drug effects, duration of effects, and general time course of effects and is a widely used and accepted approach in laboratory studies of drug effects. During the final assessment each day, subjects will complete a Drug vs. Money Questionnaire to indicate the dollar value they would place upon the drug received⁹⁸, which is a well-accepted proxy measure of abuse liability. Study staff will document adverse events throughout the study and any subject who experiences a strongly unpleasant effect of the medications, or wishes to discontinue for any reason will be able to end participation at any time. Any subject who is experiencing strong agonist effects at the end of the session will be provided overnight accommodation in the Clinical Research Unit (CRU; which is located on our campus and with whom we have frequent collaborations); based on our experience we expect this to be rare and are budgeting for 20% of sessions to undergo a one-night CRU stay.

Measures

Pilot testing indicates it takes approximately one hour to complete the assessment battery (see Table 2).

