2005). Currently, many pain research laboratories are exploring the associations of common genetic variants in humans with pain sensitivity or clinical pain conditions by evaluating common single nucleotide polymorphisms (i.e., sites in the genome where the DNA sequences of many individuals differ by a single base) located on pain-relevant genes (Diatchenko, Slade et al. 2005;Diatchenko, Nackley et al. 2006). For example, genetic variability at sites coding for a particular opiate receptor are primary candidates for genetic influences on pain since this receptor is the principal site of action for both endorphins and exogenous opioids (Lotsch, Skarke et al. 2004).

At present, the field of human pain genetics is in its infancy; a handful of putative pain-relevant polymorphisms have been identified, but positive findings have often failed to replicate, and new polymorphisms are expected to be identified over the next several years (Edwards 2006). Thus, we will evaluate several current candidate pain genes, and will also store participants' samples for future evaluation as more information becomes available regarding which polymorphisms are likely to play a role in shaping individual differences in the perception and experience of pain. The SNPs that we will evaluate based on the current literature are in the genetic regions coding for the Catechol-O-Methyltransferase gene, the mu opioid receptor gene, the delta opioid receptor gene, and the interleukin-1 and interleukin-6 genes.

- b. Study duration and number of study visits required of research participants.

Participants will complete one screening visit and four experimental session visits.

- c. Blinding, including justification for blinding or not blinding the trial, if applicable.

Participants and staff will be blinded to both the drugs and the doses of study medications being administered at each study visit. This will allow a rigorous test of the study hypotheses by not biasing participants or staff towards differential pain ratings. This is an essential component of the study. As described, we will inform participants that they may receive a combination of FDA-approved stimulants, benzodiazepines, opioids, cannabinoids, over-the-counter medications or placebo, though the participants will not actually be receiving stimulants, benzodiazepines, or over-the-counter drugs.

- d. Justification of why participants will not receive routine care or will have current therapy stopped.

N/A

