a. Protection Against Hydromorphone Risks: We have extensive experience in the administration of hydromorphone and other opioid agonists in controlled laboratory settings and therefore anticipate few problems. Any individual who may be prone to the risks associated with hydromorphone will be excluded from participating. Although research staff and participants will be blinded to the exact medication provided, both groups will be informed of the potential side effects and risks associated with the study drug administration. Participants will be free to discontinue study participation at any time without consequence. The dose of hydromorphone that is being administered is consistent with clinical care, and is a medium level dose for the treatment of pain. Hydromorphone will always be administered along with placebo in the first session, which will provide a valuable opportunity to exclude from further participation any participant who experiences untoward effects (e.g., nausea, vomiting) resulting from that dose of hydromorphone. Great care has been taken in selecting the appropriate drug doses to ensure hydromorphone is well-tolerated and safe for our participants and participants will also be able to discontinue study participation at any time. The most serious risk associated with hydromorphone administration is respiratory depression. We believe this risk is minimal in this study for several reasons. First, we are administering a mid-level dose and have

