d. Protection Against Risks of Discomfort from Pain Testing: It is likely that participants will experience some acute and transient discomfort from the pain testing session, however we will work to mitigate that risk as much as possible. First, participants will be informed of the pain testing procedure during the informed consent and will be able to make an informed decision regarding their study participation. Second, we chose standardized pain tests that are known to produce short-lived effects and thus are unlikely to produce any residual pain. Third, the measures rely on the participant ending the pain testing procedure as an outcome measure, which means that all participants are encouraged to remove themselves from the painful stimulus at any time and that they are in control of the magnitude and duration of pain they experience. Fourth, we will enforce an upper limit on all pain measures to prevent any tissue damage from occurring (e.g., hand cannot be in cold pressor task for >300 seconds). Fifth, participants will be informed that they can revoke their consent to participate in the pain testing at any time without penalty. Specific to capsaicin- one of the primary risks of capsaicin is that it could be accidentally transferred to another part of the body. To prevent this from happening, we will make sure the exposure site is well-marked and that all residual topical cream is removed with alcohol pads once the cream has been mostly absorbed. We will also be able to apply ice to the exposure site to reduce any persistent discomfort associated with capsaicin. Finally, the participants will be monitored by study staff and will have access to medical care and concomitant medications to treat residual pain if necessary. We will also document and submit to our IRB all adverse events reported from the pain testing session and will follow any recommendations they may have regarding the cessation of pain testing. Across hundreds of research participants with various conditions, we have had no adverse events deemed greater than mild (even this level AE occurs in < 1/100 cases) related to the use of these devices.

e. IV Placement and Blood Draws: These procedures are routinely performed without incident in medical settings and will be performed by a certified phlebotomist. Additionally, these procedures will only occur in a subset of participants that volunteer to undergo these procedures and can be stopped at any time without penalty.

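### Hyp4 counts only adverse events judged related, yet its opioid-alone reference is always session 1 and can be identified from the protocol, so attribution may differ between the two sides of the contrast

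*Combined protocol and SAP*

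**What the plan says.** **Endpoint.** Section 7.a, Aim 3, assesses Hyp4 by "summing the mean number of related mild, moderate, and severe adverse events (separately", and then "using 1 factor models to assess a main effect of Drug". The plan does not define related, does not name who decides it, and lists no Hyp4 analysis of events regardless of cause.

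**Contrast.** Section 2, Aim 3, hypothesises that "cannabinoids will not increase adverse events (Hyp4" in comparison with opioids alone. The opioid-alone condition is therefore the reference.

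**Session order.** Section 4.a (Study Design Overview) states: "Oral hydromorphone will be administered in the first session". Section 8.b (Protection Against Hydromorphone Risks) confirms it: "Hydromorphone will always be administered along with placebo in the first session". Tables 1a and 1b place this condition above the randomized block, and the Experimental Sessions text describes the capsules as "randomized in sessions 2-4".

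**Blinding.** Section 4.c states: "Participants and staff will be blinded to both the drugs and the doses of study medications being administered at each study visit". Section 4.a adds that staff are kept unaware of which medications are under study and that the pharmacy manages the randomization and blinding.

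**Who handles adverse events.** Under section 4.a, study staff document them throughout. Under section 8.c, the principal investigator and co-investigators report them.

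**The concern.** A filter on judged relatedness is harmless to a comparison only if the judgement is made on the same footing in every condition. Here it may not be. A rater who knows the protocol knows that a session 1 event followed hydromorphone. For an event in a later session, the same rater cannot tell placebo, dronabinol and the combination apart. The session that can be identified is the Hyp4 reference.

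At stake is the safety conclusion on adding a cannabinoid to an opioid. If the related share differs between session 1 and the combination session, the Hyp4 comparison mixes a drug difference with an attribution difference, and the planned analysis cannot separate them. This problem comes from the endpoint definition. It is additional to any effect of the fixed order itself, and it can be removed without touching the order.

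**Working it through.** The documents give no event rate, attribution rate, margin or power for Hyp4, so there is no stated figure to reproduce. The check has two parts.

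**1. What a rater who knows the order would know**

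| | Session 1 | Sessions 2 to 4 |
|---|---|---|
| Possible conditions | Hydromorphone with placebo | Placebo, dronabinol, or the combination |
| Chance that an active drug was given | 1 | 2/3 |
| Chance that an opioid was given | 1 | 1/3 |

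The later-session chances are for one session taken at random, before any effect is seen. They follow from sections 4.a and 8.b and from Tables 1a and 1b. For such a person, the section 4.c statement cannot hold in session 1. Section 8.b (Protection Against Dronabinol Risks) likewise says staff are blind to when the combination session occurs, although it can never be session 1.

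**2. How unequal attribution carries into the result**

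Let RR be the true ratio of event counts, combination to opioid alone. Let s_H and s_C be the shares of events called related under the opioid alone and under the combination. Then

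observed ratio = RR × s_C / s_H.

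All three inputs are assumptions. With RR = 1.3:

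| s_H | s_C | Calculation | Observed ratio |
|---|---|---|---|
| 0.80 | 0.80 | 1.3 × 0.80 / 0.80 | 1.30 (undistorted) |
| 0.95 | 0.80 | 1.3 × 0.80 / 0.95 | 1.09 (shrunk) |
| 0.95 | 0.70 | 1.3 × 0.70 / 0.95 | 0.96 (hidden) |
| 0.80 | 0.95 | 1.3 × 0.95 / 0.80 | 1.54 (exaggerated) |

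A true increase disappears once s_C / s_H falls to 1/RR: 1/1.2 = 0.83, 1/1.3 = 0.77, 1/1.5 = 0.67. With no true difference (RR = 1), shares of 0.95 and 0.70 give 0.74, and shares of 0.80 and 0.95 give 1.19.

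Equal shares leave the ratio intact, whatever their level. Only a difference between the shares matters, and counting events regardless of relatedness sets both shares to 1.

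**The case against.** The strongest reply is that the mechanism is inferred. No section says who assigns relatedness or that this person knows the session order, and section 4.a says staff are blinded to the medications under study. That stands, and it is why the point is conditional. Against it, section 8.b treats session 1 as a chance to exclude participants with untoward effects of hydromorphone, which requires someone to attribute session 1 events to that drug. The investigators who report events would also know the protocol. Nothing separates these people from whoever judges relatedness.

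A reader might infer that the filter favours the sponsor's hypothesis, because session 1 events would be called related more readily. The documents do not establish that direction. Sections 7.d, 8.a (Opioid-Cannabinoid Interactions) and 8.b show particular concern about tachycardia with the combination, which could raise attribution in sessions 2 to 4. Section 8.a also reports no moderate or serious effects with hydromorphone in a study of opioid-naive participants, which could lower expectations for session 1.

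A reader might also see the pain tests as rival explanations for nausea or dizziness. Section 8.a lists mainly local effects for these procedures and neither of those symptoms. Section 8.b puts device-related events, none above mild, at under 1 in 100 cases. That section does promise to "document and submit to our IRB all adverse events reported from the pain testing session", but this concerns reporting and says nothing about attribution.

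Related might also mean related to the study, not to the drug. The plan leaves this open.

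Finally, harm could show elsewhere: self-reported negative effects, bad-effect ratings and vital signs pass through no relatedness filter. That is true, but none of them is the Hyp4 adverse event count.

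**Conclusion.** The point holds in a limited form. It is established that Hyp4 counts only related events, that its reference condition is always session 1, that anyone who knows the protocol can identify that session, and that section 4.c says otherwise. It is possible, but not shown, that the person judging relatedness has this knowledge. If so, the Hyp4 ratio may be distorted in either direction.

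No size can be given. The range from 0.96 to 1.54 around a true 1.3 only illustrates assumed shares. A one-sided choice, such as 0.90 for the opioid and 0.60 to 0.75 for the combination, gives 0.67 to 0.83 under equal true rates (0.60/0.90 and 0.75/0.90). That could be misread as a predicted 17 to 33% understatement, but those shares have no source in the documents. Nor do the documents support saying that staff are in fact unblinded. The combination itself stays masked by design among sessions 2 to 4.

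**What to change.** **Section 7.a.** Make the main Hyp4 count all adverse events that start or worsen after dosing in a session, by severity and regardless of judged relatedness. Keep related events as a supporting analysis, and state there what related means and who decides it.

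**Section 4.c.** Reconcile the blinding statement with the fixed first session, for example by saying that the session 1 condition can be known to anyone familiar with the protocol.

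**Cost.** A few sentences. Adverse events are already documented throughout the study, so no new data are needed, and no dose, session order or participant management changes. Unrelated and procedure-related events will add some noise to the count. For pain testing this should be low, given the rate in section 8.b.

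**What this does not cure.** Opioid alone remains confounded with the first session. Participants may still be excluded after session 1 before receiving the combination. A non-significant Drug effect without a margin still cannot show that there is no increase. Severity grading also remains a judgement by observers who may know the order. These need separate attention.
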